Upon receipt of all required regulatory and IRB/EC approvals, completion of protocol registration procedures with the DAIDS Regulatory Compliance Center, and activation by the HPTN Coordinating and Operations Center, the protocol modifications listed below will be implemented. Detailed modifications of the protocol text are indicated by ~~strikethrough~~ (for deletions) and **bold** (for additions).

Detailed Listing of Modifications

1. On the Cover Page, added new Investigator:

**Protocol Co-Chair
[name]
University of Alabama at Birmingham
Birmingham, Alabama, USA**

2. In the list of Abbreviations and Acronyms, added the following acronyms:

BLHC	Bronx-Lebanon Hospital Center
CBO	community based organization
IFA	Immuno-fluorescent antibody
UAB	University of Alabama at Birmingham (site)

3. In the Protocol Team Roster:

[name]
~~Prevention Research Specialist~~ **HPTN CORE Protocol Specialist**
Family Health International
[name]
[name]
[contact]
[contact]

**[name]
Principal Investigator/Protocol Co-Chair
University of Alabama at Birmingham
[name]
[name]
[contact]
[contact]
Email: [contact]**

[name], BSc (Pharm)
HPTN CORE Protocol Specialist
Family Health International
[name]
[name]
[contact]
[contact]
Email: [contact]

[name]
Investigator
University of Alabama at Birmingham
[name]
[name]
[contact]
[contact]
Email: [contact]

[name]
~~Protocol Operations Coordinator~~ **SDMC Project Manager**
SCHARP – FHCRC
[name]
[name]
[name]
[contact]
[contact]
Email: [contact]

~~[name]~~ **[name]**
Protocol Behavioral Scientist
Division of Health and Behavior Sciences
Family Health International
[name]
[name]
[contact] [name]
[contact]
E-Mail: ~~[contact]~~ **[contact]**

4. In the Protocol Schema:

Design: Phase II, four arm, ~~two~~ **three** site, randomized, double blind, controlled trial comparing tenofovir 1 % vaginal gel or placebo gel used once daily and tenofovir 1% vaginal gel or placebo gel used prior to intercourse, with 24 weeks of product exposure and follow up. Participants with chronic hepatitis B virus (CHBV) will have an additional 12 weeks follow up.

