~~Throughout the period of study implementation and data analysis, neither study sStudy staff, nor participants will be informed of the participants' random assignments of all study products. Both study gels will be supplied in identical, single-use tubes, and single use applicators packaged in individual wrappers. Study staff and participants will be unblinded after all study visits and data analyses are completed. Individual exceptions may be considered by the Protocol Chair and Medical Officer in situations where product information may be needed to protect the safety of the participant.~~

Blinding will be maintained (with the exception of Study Pharmacy Staff) until all data are entered into the study database, all study endpoint data and other data included in the final analysis have been cleaned and verified, and the data are ready for final analysis. This will be explained to participants as part of the study.

There are no circumstances under which it is expected that unblinding will be necessary for the provision of medical treatment or to otherwise protect the safety of study participants. As described in Section 4.8, in the event that an Investigator is concerned that a participant might be put at an undue risk by continuing product use, the Investigator may discontinue use by this participant; however, knowledge of the specific product to which the participant was assigned should not be necessary to guide further follow-up and/or treatment. If an Investigator feels that specific product knowledge is necessary to protect participant safety, the Investigator will notify the PSRT to consider and rule upon the request.

39. In Protocol Section 7.6.2 "Analysis of PK Data", clarified instructions for collecting PK specimens at Weeks 4, 12 and 20 visits:

Blood levels of tenofovir will be evaluated after vaginal administration. Specimens from participants receiving placebo gel will not be assayed. A single tenofovir blood level will be drawn at the Week 4, 12 and 20 visits. **For the Weeks 4 and 12 visit specimens the participants will not be instructed to insert the study gel prior to these visits, and the analysis will be performed in an exploratory way by investigation plasma concentrations of tenofovir during terminal elimination**

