(~~weeks 4 and 12 approximately~~ **Blood draws are estimated to occur** 12-16 hours post-dose, depending on an individual participant's study gel use). **For the Week 20 visit specimen,** ~~the analysis will be performed in an exploratory way, by investigating plasma concentrations of tenofovir during the peak absorption period following dosing,~~ **however at this visit, all participants will be instructed to insert the study gel prior to the visit, so that blood will be drawn** approximately 2-6 hours post-dose, the period coinciding with peak concentrations in previous studies [HPTN 050]) ~~and much later is the dosing interval~~ Tenofovir blood levels will be further investigated by correlating serum tenofovir levels with HSV-2 serostatus, the presence or absence of genital tract inflammation, and frequency of sexual activity.

40. In Protocol Section 8.3, Risks, third paragraph, second sentence, revised to match updated references:

Although 92% of participants reported at least 1 AE, 87% of those reported AEs were mild, and ~~77~~**70**% of the AEs were limited to the genitourinary tract. Four severe AEs were reported, with only one, lower abdominal pain, thought to be product-related⁶

41. In Protocol Section 8.3, Risks, seventh paragraph, last bullet, and, first sentence of eighth paragraph:

- Changes in bone growth and strength were seen in study animals given tenofovir. It is unknown if long term use of ~~taking tenofovir gel for a long time~~ will cause bone abnormalities in adults. ~~In children, some decrease in bone thickness (density has been seen).~~ **Bone thinning has been seen in adults and children taking oral tenofovir**

Tenofovir and its oral form (~~TDF~~) administered in systemic dose toxicology studies to rats, dogs and monkeys at exposures

42. In Protocol Section 8.6, Participant Confidentiality, third paragraph, second sentence revised to:

A Federal Certificate of Confidentiality will be sought for this study. The Certificate applies in the US **sites** only (~~i.e. the New York site~~) and will protect study staff from being compelled to disclose study related information by any Federal, State or local civil, criminal, administrative, legislative, or other proceedings.

43. In Protocol Section 9.1, revised second bullet and added last bullet:

- blood for HIV, ~~HSV-2~~, syphilis serology and HBsAG
- **blood for HSV-2 (India only)**

44. In Protocol Section 9.2, added last bullet to:

- **Blood for HSV-2 (US sites only)**

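### The 12-16 h post-dose description of the Week 4 and 12 PK draws does not suit the coitally dependent regimen, where sexual frequency is tied to time since last dose and confounds the planned correlation

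*Supplement*

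**What the plan says.** The Protocol Schema (amendment item 4) has two regimens: once-daily gel, and "tenofovir 1% vaginal gel or placebo gel used prior to intercourse". Section 7.6.2 (item 39) covers the tenofovir levels. Only women on active gel are assayed, with a single sample at each of Weeks 4, 12 and 20.

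- **Weeks 4 and 12:** "the participants will not be instructed to insert the study gel prior to these visits". The draws are estimated to fall "12-16 hours post-dose, depending on an individual" participant's gel use. The aim is stated as follows: "the analysis will be performed in an exploratory way by investigation plasma concentrations of tenofovir during terminal elimination".
- **Week 20:** all participants are instructed to insert gel beforehand, so that blood is drawn about 2-6 h after the dose. Section 2.4.1 (item 12) words this instruction separately for the daily and the coitally dependent arm.
- **Associations:** levels are to be correlated with HSV-2 serostatus, "the presence or absence of genital tract inflammation, and frequency of sexual activity". The text shown does not say which visit is used, whether the regimens are separated, or whether time since dose is taken into account.

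**The concern.** A daily user doses by the clock, so one interval can describe most of her draws. A coitally dependent user doses when she has sex, so the time from last dose to an un-instructed draw can be hours or days. A single 12-16 h description does not fit both.

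The correlation is affected for the same reason. In the coital arm a woman who has sex more often has, on average, dosed more recently, and a more recent dose gives a higher level. Level and sexual frequency can then move together even if sexual activity has no effect on absorption. If the association is computed from Weeks 4 and 12, or with the regimens pooled there, it could be misread as an absorption effect. Low levels in that arm could likewise be misread as low systemic uptake when they only reflect the lack of a recent dose.

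**Working it through.** **The plan's figure.** The 12-16 h estimate cannot be reproduced, because the text shown gives no visit clock time, usual insertion time or act frequency. It is plausible for a daily evening dose: insertion at 20:00 and a draw between 08:00 and 12:00 gives 12 to 16 h (clock times assumed).

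**Share of coital-arm draws in the window.** Let k be acts per week. This is assumed, so a range is shown.

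- *Evening acts only*, at most one per evening, with the draw about 14 h later: P(dose the evening before) = k/7. Otherwise the last dose is at least one day older, about 14 + 24 = 38 h, or at least about 36 h allowing 2 h either way.
- *Acts at random times* (Poisson, rate k/168 per hour): P(12-16 h) = exp(-12k/168) - exp(-16k/168). Median time since dose = ln 2 × 168/k.

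| k per week | Evening acts: in window | Random times: in window | Random times: median time since dose |
|---|---|---|---|
| 1 | 1/7 = 14% | 0.931 - 0.909 = 2.2% | 116 h |
| 2 | 2/7 = 29% | 0.867 - 0.827 = 4.0% | 58 h |
| 3 | 3/7 = 43% | 0.807 - 0.751 = 5.6% | 39 h |
| 4 | 4/7 = 57% | 0.751 - 0.683 = 6.8% | 29 h |

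Only with an act every evening (7/7) does the window describe every draw.

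**Effect on the correlation.** The coital arm was simulated with 200,000 women per scenario and no true effect of frequency on level.

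- From Section 1.3.2 (item 8): median peak 3.4 ng/mL and limit of quantitation 3.0 ng/mL, both from the earlier study.
- Assumed: lognormal peak with log-SD 0.6, peak at 2 h, half-life 4, 8 or 17 h, gamma-distributed frequency with mean 2 or 4 acts per week, and evening or random act times.

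Spearman correlations, as ranges over the scenarios:

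| | Level with frequency | Same, given time since dose |
|---|---|---|
| All levels measurable | 0.41 to 0.54 | 0.01 to 0.17 |
| Levels below 3.0 ng/mL set to zero | 0.01 to 0.20 | -0.06 to 0.02 |

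**How often would a level be measurable?** Section 1.3.2 gives one decline curve, for the woman with the highest peak: 25.8 ng/mL at 2 h, 10.89 at 4 h, undetectable at 12 h.

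- Half-life over 2-4 h: 2 × ln 2 / ln(25.8/10.89) = 1.6 h.
- Half-life over 4-12 h: at most 8 × ln 2 / ln(10.89/3.0) = 4.3 h.
- For a median peak of 3.4 ng/mL at 2 h to be still 3.0 at 12 h: 10 × ln 2 / ln(3.4/3.0) = a half-life of about 55 h.
- For the second-highest peak, 7.1 ng/mL: 10 × ln 2 / ln(7.1/3.0) = about 8 h.

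In the simulation, even when every dose was 12-16 h before the draw, only 0.1%, 6.6% and 27% of samples reached 3.0 ng/mL at half-lives of 4, 8 and 17 h. At that limit most Week 4 and 12 samples would be unquantifiable under either regimen.

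**The case against.** The strongest reply is that the plan hedges. The interval is called an estimate, it is said to depend on each woman's gel use, and the analysis is exploratory. The correlation sentence follows the Week 20 text and is not limited to Weeks 4 and 12, so the plan as written already offers a sample with controlled timing. At the earlier study's limit the spurious correlation would be weak. How systemic level varies with real coital use is also a fair descriptive question.

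Much of this stands, and it rules out several stronger readings:

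- *The interval can never apply in the coital arm.* It does apply to a woman who dosed the evening before.
- *The correlation must come out positive, or mostly measures time since dose.* That needs measurable levels and little direct effect of frequency. The simulation sets the direct effect to zero.
- *Insertion and draw times are not recorded.* Only an amendment listing is shown. The full protocol or the case report forms may capture them, so their absence cannot be asserted.
- *The HSV-2 correlation mixes laboratory with region.* Items 43 and 44 list Indian and US testing under different sections (9.1 and 9.2), but Appendix I says only that HSV-2 serology is local or central. A split of laboratory by region is not shown.

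The reply leaves two things unanswered. Saying that timing depends on use admits the variation but does not handle it, and nothing in the text directs the correlation to Week 20. A weak correlation at the assay limit is no safeguard either: conditional on time since dose almost nothing remains (-0.06 to 0.02), and an unquantifiable coital-arm sample cannot be put down to low absorption rather than to no recent dose.

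**Conclusion.** The point holds in a limited form. The 12-16 h description suits the daily regimen but not the coitally dependent one unless acts are nearly daily and in the evening. At an assumed 1-4 acts per week it covers about 14-57% of that arm's Week 4 and 12 draws (evening acts) or 2-7% (random times). The planned correlation of level with sexual frequency is confounded by time since last dose if it uses those visits or pools the regimens there.

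The direction of the confounding follows from the design, but its size does not. It depends on act frequency, half-life and the assay limit: about 0.4-0.5 on the rank-correlation scale if all levels are measurable, and 0.01-0.20 at 3.0 ng/mL. This trial's own assay limit is not shown. If allocation is equal, which is also not shown, half of the active-gel women are in the affected regimen.

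A reader might infer that the trial's main safety conclusions are at risk. The documents do not support that: the analysis is exploratory, and Week 20, with an instructed dose in both regimens, largely avoids the problem. The change is worth making because it is cheap and the text, followed literally, allows a misleading result.

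**What to change.** In Section 7.6.2:

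1. State the 12-16 h estimate for the daily regimen only. For the coitally dependent regimen, say that time since last dose is variable and will be reported.
2. Analyse Week 4 and 12 levels separately by regimen, with time since last dose as a covariate, and name a method for values below the limit of quantitation.
3. Confirm that the date and time of the last insertion and of the blood draw are captured at each PK visit. If they are not, add these fields before sampling, since insertion times are hard to recover later.
4. Base the sexual-frequency correlation on the Week 20 pre-dosed sample or on the daily arm. A descriptive summary of levels under actual coital use can remain, labelled as exposure rather than absorption.

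The cost is a few sentences of analysis text and, if times are not yet captured, the time fields on the PK form. The downside is a smaller sample for the exploratory sexual-frequency question.
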